9.5. VITAL SIGNS

Vital signs will be measured at the screening visit (Week -11), both visits of run-in (Week -2 and Day -3 to -5), and at weeks 2, 4, 6, 12, 24, 36, 48, and 60. Measurements of vital signs will include measurement of supine, sitting and standing blood pressure (BP) measurements, and heart rate. Only the BP measured in the sitting position will be used to determine eligibility. Orthostatic systolic and diastolic BP will be calculated as supine measurement - standing measurement.

For BP, pulse rate, and respiration rate, observed values and change from baseline will be summarized by treatment group and mapped visit using descriptive statistics (n, mean and median, standard deviation, minimum and maximum). BP summary will include supine, sitting, standing and orthostatic BP. Safety analysis set will be used for table summary.

9.6. ELECTROCARDIOGRAM

A 12-lead electrocardiogram (ECG) will be conducted at the screening visit (Day - 11), on baseline visit (Day -3 to -5), at weeks 24, 60, and 96. ECG parameters measured will be the RR interval, PR interval, QRS duration, QT interval, and QTcB. Each ECG should also be assessed by the investigator for signs of ischemia, clinically significant hypertrophy, and clinically significant T-wave abnormalities or arrhythmia.

If a subject's ECG parameters cannot be determined due to pacemaker placement or atrial fibrillation, the ECG parameters will be considered missing. Any machine generated values such as 0 or 9999 will be excluded from the analyses.

For each abnormal ECG result, the investigator shall ascertain if the observation represents a clinically significant change from the screening ECG for that individual subject (this determination, however, does not necessarily need to be made the first time an abnormal result is observed. The investigator may repeat the ECG to verify the results of the original result). If the ECG result is determined to be a clinically significant and abnormal change from baseline for that subject, it is considered an AE.

For the ECG parameters, observed values and change from baseline from scheduled visits will be summarized with descriptive statistics by treatment group and overall at each visit. The maximum change from baseline from scheduled visits will also be provided for ECG parameters.

For the ECG overall assessment, the number and percentage of subjects in each overall assessment category (normal, abnormal but not clinically significant, abnormal and clinically significant, missing) will be presented by treatment group and overall at each visit.

9.7. PHYSICAL EXAMINATION

A complete physical examination will be conducted at the baseline visit (Day -3 to -5) and at weeks 60, and 98. The examination will include measurement of body weight, and a general assessment of all body systems including the skin, head, eyes, ears, nose, throat, neck, heart, lungs, abdomen, lymph nodes, and extremities. An abbreviated physical examination will be conducted at screening visit 1 (Week -11) and at weeks 6, 24, 36, 48, 72, and 96 or clinically indicated. The examination will include body weight and height (height will be measured only at screening), and general assessment of the skin, heart, lungs and abdomen. Physical examination findings will be presented in a by-subject listing.

10. HEALTH RELATED QUALITY OF LIFE ASSESSMENT

Health related quality of life will be assessed by EQ-5D-3L. It will be performed on Day 1, Weeks 24, 60, and 96.

The EQ-5D is a standardized measure of health status developed by the EuroQol Group in order to provide a measure of health for clinical and economic appraisal. The questionnaire consists of 2 components: the EQ-5D descriptive system and the EQ visual analogue scale (EQ VAS). The EQ-5D descriptive system is comprised of the following five dimensions: mobility, self-care, usual activities, pain/discomfort and anxiety/depression; each dimension has 5 possible responses scored from 1 (unimpaired) to 5 (most impaired). The EQ VAS records the respondent's self-rated overall health on a vertical, visual analogue scale where the endpoints are labeled, "Best imaginable health state" and "Worst imaginable health state". Health states in the EQ-5D-3L can be converted into a single index value, where index values are presented in the country specific value sets to facilitate the calculation of quality-adjusted life years (QALYs). EQ-5D-3L value sets can be used to obtain the EQ-5D-3L index values based on the UK version. The index score in this version range from -0.594 to 1 with higher score indicating better quality of life. To compute the value of any health state, first of all a value of 1 is assigned for the 11111 status (without health problems in any dimension). If the status is different to 11111, the constant value is subtracted (see below table). Later, if at least one moderate problem (value of 2 reported in the database) is reported in any of the dimensions, the correspondent dimension value is subtracted. The same procedure is followed when there is at least one extreme problem (value of 3 reported in the database), but multiplying by 2 the appropriate constant value. Finally, if at least one extreme problem is reported then the N3 value is subtracted.

Parameter	Coefficient (UK)
Constant	-0.081
Mobility=2	-0.069
Mobility=3	-0.314
Self care=2	-0.104
Self care=3	-0.214
Usual activities=2	-0.036
Usual activities=3	-0.094
Pain/discomfort=2	-0.123
Pain/discomfort=3	-0.386
Anxiety/Depr.=2	-0.071
Anxiety/Depr.=3	-0.236
N3	-0.269

Descriptive statistics will be presented for each item of the questionnaire, the EQ-5D-3L index score and VAS for ITT analysis. Both actual values and changes from baseline will be summarized by treatment group for each visit. In addition, the treatment effect for change from baseline in index score and VAS will be assessed using the MMRM model in Section 8.1.1 as template. The model will include treatment, visit, treatment-by-visit interaction and randomization stratification factors, including baseline HbA_{1c}, as the fixed effects terms and the baseline EQ-5D-3L index score (or VAS) as covariate. All analysis will be based on ITT analysis set.

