4.5. OTHER ENDPOINTS

- Health-related quality of life instrument, EQ-5D-3L

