8.2. SECONDARY EFFICACY ENDPOINT(S) AND ANALYSES

The secondary endpoints will only be tested when the non-inferiority of the primary efficacy assessment is established at one-sided significance level of 0.025. To control the overall type I error of 0.05, the secondary efficacy objectives will be tested at one-sided 0.025 significance level following the sequence below:

- Superiority test of the change in body weight in subjects with baseline body mass index (BMI) ≥ 25 kg/m² at week 60.
- Superiority test of the change in SBP in subjects with baseline SBP ≥ 140 mmHg from baseline at week 60.
- Superiority test of the difference in proportion of subjects with ≥ 1 severe or documented symptomatic hypoglycemia events over 96 weeks

Analysis for secondary endpoints will be based on ITT analysis set and repeated for PP analysis set. For body weight and SBP, all post-baseline values up to week 60 will be used for model analysis. All values will be summarized.

8.2.1. Change in body weight in subjects with baseline body mass index (BMI) ≥ 25 kg/m² at week 60

This will be tested if the non-inferiority of HbA_{1c} and the previous secondary efficacy endpoints are significant. Data after rescue medication will not be excluded. The comparison of change in body weight between randomized treatments at week 60 will be carried out using the similar MMRM model as section 8.1.1 using all available data. The model will include terms for region, treatment, baseline HbA_{1c} as continuous variable, treatment background (metformin-only or metformin-and-OHA), and baseline eGFR (≥ 90 or < 90 mL/min/1.73 m²) as fixed effects and the corresponding baseline weight value as covariate. Treatment comparison p-values and difference at week 60 will be estimated from the model, with the two-sided 95 % CIs of the treatment difference also presented. If the superiority of HbA_{1c} is not established, the nominal p-value will not be used for inferential purposes. Summary table will be presented and figures will be displayed for ITT population.

8.2.2. Change in SBP in subjects with baseline SBP ≥ 140 mmHg from baseline at week 60

This will be tested if the change from baseline body weight is significantly different between bexagliflozin and glimepiride groups based on ITT analysis set for subjects with a BMI ≥ 25 kg/m². Change from baseline in SBP at week 60 will be analyzed in a similar manner as change in body weight, Section 8.2.1, based on ITT analysis set for all

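### SAP section 10 contradicts itself on EQ-5D-3L level-3 scoring: the printed coefficients used once give the stated range, but the text tells the programmer to multiply by 2

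*SAP*

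**What the plan says.** SAP section 10 scores the EQ-5D-3L index with the UK value set and gives three pieces of information.

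- **A range.** "The index score in this version range from -0.594 to 1 with higher score indicating better quality of life".
- **A coefficient table.** It has a constant, separate level-2 and level-3 values for each of the five dimensions, and an N3 term.
- **A written algorithm.** State 11111 is given the value 1. For other states, "If the status is different to 11111, the constant value is subtracted (see below table"). Each level-2 response then takes off its dimension's value. The same is done for an "extreme problem (value of 3 reported in the database), but multiplying by 2 the appropriate constant value". The last step is "Finally, if at least one extreme problem is reported then the N3 value is subtracted".

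Later in the same section, "the treatment effect for change from baseline in index score and VAS will be assessed using the MMRM model", with the baseline index as a covariate. SAP section 4.5 lists "Health-related quality of life instrument, EQ-5D-3L" among the other endpoints. The formal sequence in SAP section 8.2, where "the secondary efficacy objectives will be tested at one-sided 0.025 significance level following the sequence below", covers body weight, systolic blood pressure and hypoglycemia only.

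**The concern.** The table already holds a complete coefficient for every level-3 response (mobility at level 3 is 0.314 in absolute value, for example), so nothing is left to double. The clause also does not define the value to be multiplied. It could be the level-3 coefficient, the row labelled Constant, the level-2 coefficient or the N3 term. SAP section 10 is the only place in the two documents that sets out a scoring rule. Two programmers could therefore derive different indices from the same questionnaire.

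At stake is the derived index at every subject-visit with at least one level-3 response, and through it the MMRM estimate of the treatment effect on the index. The VAS, the item responses, and the primary and key secondary endpoints do not depend on this rule.

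**Working it through.** **Inputs** (SAP section 10, absolute values).

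| Term | Level 2 | Level 3 |
|---|---|---|
| Mobility | 0.069 | 0.314 |
| Self care | 0.104 | 0.214 |
| Usual activities | 0.036 | 0.094 |
| Pain/discomfort | 0.123 | 0.386 |
| Anxiety/depression | 0.071 | 0.236 |
| Sum | 0.403 | 1.244 |

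Constant 0.081; N3 0.269.

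**1. Reproducing the stated range.** With each coefficient used once, the index is 1 for 11111. Otherwise it is 1 - 0.081 - (sum of dimension values) - 0.269 if any dimension is at level 3.

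- 33333: 1 - 0.081 - 1.244 - 0.269 = -0.594
- 11111: 1

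Over all 243 states the minimum is -0.594 and the maximum is 1, exactly as the SAP states.

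**2. Applying the doubling.** Four readings of the clause:

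- A: level-3 values doubled
- B: the constant doubled when a level 3 is present
- C: twice the level-2 value in place of the level-3 value
- D: N3 doubled

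| | Table once | A | B | C | D |
|---|---|---|---|---|---|
| 33333 (minimum) | -0.594 | -1.838 | -0.675 | -0.156 | -0.863 |
| 11131 | 0.264 | -0.122 | 0.183 | 0.404 | -0.005 |
| Change, 11121 to 11131 | -0.532 | -0.918 | -0.613 | -0.392 | -0.801 |

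Arithmetic for 33333:

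- A: 1 - 0.081 - 2×1.244 - 0.269
- B: 1 - 2×0.081 - 1.244 - 0.269
- C: 1 - 0.081 - 2×0.403 - 0.269
- D: 1 - 0.081 - 1.244 - 2×0.269

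For 11131 the table gives 1 - 0.081 - 0.386 - 0.269 = 0.264. A takes off a further 0.386, B a further 0.081 and D a further 0.269. C gives 1 - 0.081 - 2×0.123 - 0.269 = 0.404. State 11121 is 1 - 0.081 - 0.123 = 0.796 throughout, because it has no level 3.

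Nine further combinations were tried: several terms doubled together, or two extra constants subtracted once or per level-3 dimension. Their minima are -1.919, -0.756, -1.404, -0.944, -2.107, -2.188, -0.237, -0.425 and -0.506. None gives -0.594.

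**3. How many states are affected.** States without a level 3 number 2^5 = 32, so 243 - 32 = 211 contain one. A, B and D lower the score in all 211. C raises it in all 211, because twice the level-2 value is below the level-3 value in every dimension (the closest is self care, 0.208 against 0.214).

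**4. Is the doubling already in the table?** The ratios of level 3 to level 2 are 4.55, 2.06, 2.61, 3.14 and 3.32, so the clause does not describe how the printed values were built.

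**5. Effect on the treatment comparison.** A subject with the same level-3 pattern at both visits has no error in change from baseline, and equal patterns in the two arms largely cancel. The documents give no frequency of level-3 responses, so the following is an assumption: the change in the share of subjects in state 11131 is larger by d = 0.01 to 0.02 in the bexagliflozin arm. The unadjusted treatment difference then shifts by d times the scoring error for that state:

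- A: d × (-0.386) = -0.0039 to -0.0077
- B: d × (-0.081) = -0.0008 to -0.0016
- C: d × (+0.140) = +0.0014 to +0.0028
- D: d × (-0.269) = -0.0027 to -0.0054

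If the arms do not differ, the shift is about zero. This calculation ignores the baseline-index covariate in the MMRM.

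**The case against.** The strongest reply is that the contradiction is unlikely to reach the results.

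- **The paragraph exposes the fault.** The clause cannot be executed without choosing a reading, and the range printed beside it rejects every reading tried.
- **There is another source.** The SAP reference list cites an EQ-5D index calculator and a value-set user guide, and SAP section 16 requires quality control of all SAS programs and output.
- **Not all readings are equally natural.** D sits badly with the separate sentence on N3, and C discards five printed coefficients. C is also the only one of the four that raises the score.
- **The consequence is small.** The 1 to 2 point scenario is not drawn from the documents, and its largest shift is 0.008 on a scale running from -0.594 to 1. The endpoint carries no formal test.

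Much of this stands as a limit on importance: a careful programmer may well score correctly, and the scenario is illustrative only. It does not remove the contradiction. The cited references print no rule in these documents, and general quality control checks a program against a specification that is itself inconsistent here. A and B, the two most natural readings, both give wrong scores.

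**Conclusion.** The concern holds. The table and the stated range agree with each other to three decimals, and the multiplication clause is the part that does not fit. Followed under any of the four readings, it gives a wrong index for every subject-visit with a level-3 response. The error in state 11131 runs from -0.386 to +0.140, depending on the reading.

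The reach is limited to the EQ-5D-3L index and its MMRM. The effect on the treatment difference cannot be sized from the documents. Under the stated assumption it is at most about 0.008 in absolute value, and about zero if level-3 patterns are alike in both arms. The conclusion that the passage contradicts itself needs no assumption. Readings beyond those tried may exist. This should be corrected, but it does not threaten the trial's main conclusions.

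**What to change.** In SAP section 10, delete the multiplication clause and state the rule in full:

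- index = 1 for state 11111;
- otherwise, index = 1 - 0.081, minus the absolute tabulated value for each dimension at level 2 or 3, minus 0.269 once if any dimension is at level 3.

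The word *absolute* matters. The table prints the coefficients as negative numbers while the text says to subtract them, which taken literally gives 1 + 0.081 + 1.244 + 0.269 = 2.594 for 33333.

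Check the scoring program against three known states: 33333 = -0.594, 11131 = 0.264, and 22222 = 1 - 0.081 - 0.403 = 0.516. The first alone exposes all four readings, and the last confirms the level-2 scoring.

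In the same edit, correct the description of the instrument. The SAP says "each dimension has 5 possible responses scored from 1 (unimpaired) to 5 (most impaired"), whereas protocol section 6.16 and the coefficient table use three levels. This changes no score.

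The cost is SAP wording and a three-state program check. Data collection, design and sample size are untouched.

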11. INTERIM ANALYSES

No interim analyses are planned.

12. DATA AND SAFETY MONITORING BOARD

An independent data and safety monitoring board (DSMB) will review descriptive summaries of accumulating safety, subject disposition and limited efficacy data every 6 months, or a frequency recommended by the DSMB.

A designated statistician who is not involved with the study operation will hold the treatment codes. The unblinded treatment information can be provided to the DSMB to facilitate the evaluation of any clinically important increase in the rate of a serious suspected adverse reaction or to the designated safety contact when the treatment information is required to determine if an expedited safety report must be submitted to regulatory agencies. The data outputs for this review will be created by an unblinded team. Personnel involved in the conduct of the study will not participate in the preparation of these outputs, receive the data, or participate in the unblinded portions of the DSMB meetings. More details will be provided for DSMB charter and DSMB SAP.

13. CHANGE FROM ANALYSIS PLANNED IN PROTOCOL

In all analysis models, continuous HbA_{1c} at baseline is used as fixed effect, in place of randomization stratification factor of HbA_{1c} group at baseline. In all models, eGFR at baseline category is used as fixed effect, in place of randomization stratification factor of eGFR at screening.

Primary analysis of the primary endpoint was MMRM using available data in the protocol. In SAP, a “retrieved dropout” analysis is used for handling missing data is used as primary analysis if data allows. Retrieve dropouts are subjects who discontinued treatment but still had their efficacy measurements at the planned visit. Sensitivity analysis of LOCF is planned in the protocol, but removed in SAP since LOCF does not add more information on sensitivity in addition to tipping point analysis.

15. PROGRAMMING CONSIDERATIONS

The following conventions will hold for programming of outputs:

- SAS® Version 9.3 or higher will be used for programming and production
- The format of the table shells will be followed as closely as possible; however, in the course of programming and familiarization with the database, some changes may become necessary. All changes will be documented. Major changes will be documented through a formal amendment to this document.
- Patients in this study will be identified as “Subjects.”
- Descriptive statistics will be displayed in the following order:

n

Mean

Standard deviation (SD)

Q1

Median

Q3

Minimum (Min)

Maximum (Max)

- Decimal places: For summary statistics, the minimum and maximum will be reported with the same number of decimal places as the collected measure, the mean, LS mean (if applicable) and median will have 1 more decimal place than the measure collected, and the SD and confidence interval (CI) will have 2 more decimal places than the collected measure. For frequency distributions, percentages will be reported to 1 decimal place. For p-values, 4 decimal places will be reported or the SAS® p-value format of “< 0.0001” or “> 0.9999” will be reported.
- Unless otherwise noted, the denominator for percentages is the number of subjects in the applicable analysis population and treatment group.
- If the frequency for a particular table cell is zero, then “0”, properly aligned, will be displayed (i.e. “0 (0.0%)” will not be displayed.)
- Non-numeric values: Where variables are recorded using < or > (e.g., “< 10”, “> 10”, “≥ 10”, or “≤ 10”) the numeric portion of the result will be used (e.g. < 10, ≤ 10, > 10, and ≥ 10 become 10) for summary; the actual recorded results, (e.g. “< 10” or “> 10”) will appear in listings.

15.1. GENERAL CONSIDERATIONS

- A separate SAS program will be created for each output.
- Output files will be delivered in Word format.
- Numbering of TFLs will follow ICH E3 guidance

15.2. TABLE, LISTING, AND FIGURE FORMAT

15.2.1. General

- All TFLs will be produced in landscape format, unless otherwise specified.
- All TFLs will be produced using the Courier New font, size 9
- The data displays for all TFLs will have a minimum 1-inch margin on all 4 sides.
- Headers and footers for figures will be in Courier New font, size 9.
- Legends will be used for all figures with more than 1 variable, group, or item displayed.
- TFLs will be in black and white (no color), unless otherwise specified
- Specialized text styles, such as bolding, italics, borders, shading, and superscripted and subscripted text, will not be used in the TFLs, unless otherwise specified. On some occasions, superscripts 1, 2, or 3 may be used (see below).
- Only standard keyboard characters will be used in the TFLs. Special characters, such as non-printable control characters, printer-specific, or font-specific characters, will not be used. Hexadecimal-derived characters will be used, where possible, if they are appropriate to help display math symbols (e.g., μ). Certain subscripts and superscripts (e.g., cm², C_{max}) will be employed on a case-by-case basis.
- Mixed case will be used for all titles, footnotes, column headers, and programmer-supplied formats, as appropriate.

15.2.2. Headers

- All output should have the following header at the top left of each page:
Theracos Sub, LLC
Protocol Number: THR-1442-C-480
- Draft or Final in top right corner.
- All output should have Page n of N at the top of each page. TFLs should be internally paginated in relation to the total length (i.e., the page number should appear sequentially as page n of N, where N is the total number of pages in the table).
- The date output was generated should appear along with the program name as a footer on each page.

15.2.3. Display Titles

- Each TLF should be identified by the designation and a numeral. (i.e., Table 14.1.1). ICH E3 numbering is strongly recommended but sponsor preferences should be obtained prior to final determination. A decimal system (x.y and x.y.z) should be used to identify TLFs with related contents. The title is centered. The analysis set should be identified on the line immediately following the title. The title and table designation are single spaced. A solid line spanning the margins will separate the display titles from the column headers. There will be 1 blank line between the last title and the solid line.

Table x.y.z
First Line of Title
Second Line of Title if Needed
ITT Analysis Set

15.2.4. Column Headers

- Column headings should be displayed immediately below the solid line described above in initial upper-case characters.
- In the case of efficacy tables, the variable (or characteristic) column will be on the far left followed by the treatment group columns and total column (if applicable). P-values will be presented in a separate comparison column (if applicable).
- For numeric variables, include “unit” in column or row heading when appropriate.
- Analysis set sizes will be presented for each treatment group in the column heading as (N=xx) (or in the row headings if applicable). This is distinct from the ‘n’ used for the descriptive statistics representing the number of subjects in the analysis set.
- The order of treatments in the tables and listings will be active treatment first, then placebo, followed by a total column (if applicable).

